5.6.5 Other Safety Analyses

5.6.5.1 Electrocardiograms

ECG assessments will be performed at Screening and at Day 1 of each cycle. Descriptive statistics for electrocardiogram parameters (HR, PR, QRS, QT, QTcB, QTcF and RR) and changes from Baseline will be presented by visit. ECG findings will be summarized. A shift table of worst postbaseline values from Baseline for ECG findings will be provided. A subject data listing will also be provided.

In addition, the number (percentage) of subjects with at least 1 postbaseline ECG result in QTc Bazett and QTc Fridericia during the treatment phase will be summarized. ECG results in QTc Bazett and QTc Fridericia will be categorized as follows:

- For subjects with Baseline and postbaseline data, maximum increase from Baseline (msec) of ≤ 30 , > 30 to ≤ 60 , and > 60
- Maximum postbaseline value (msec) of ≤ 450 , > 450 to ≤ 480 , > 480 to ≤ 500 , and > 500

5.6.5.2 Left Ventricular Ejection Fraction

The LVEF will be summarized by descriptive statistics by visit (mean, standard deviation, median, Q1, Q3, minimum, and maximum values), and percentage change from Baseline, and by percentage of reduction from Baseline (> 0 to $\leq 10\%$, > 10 to $\leq 15\%$, $> 15\%$) as well as the occurrence of subjects having a lowest postbaseline value of $< 50\%$. A subject data listing will be provided.

5.6.5.3 Lansky Play Scores or Karnofsky Performance Status Scores

Lansky play scores or KPS scores will be summarized by shifts from Baseline to worst postbaseline visit. A subject listing of Lansky play scores or KPS scores, will be provided.

5.6.5.4 Proximal Tibial Growth Plates

Radiographic findings of proximal tibial growth plates will be listed.

5.7 Other Analyses

Each question in the Palatability and Acceptability Questionnaire will be listed using the Palatability Analysis Set.

5.8 Exploratory Analyses

See [Section 5.4.3.1](#) for Exploratory Efficacy Analyses.

6 INTERIM ANALYSES

After completion of treatment in Cohort 1 and Cohort 3A, data will be reviewed with the PSC to determine the RD. In addition, the sponsor will closely evaluate the risks and benefits of the study throughout its conduct, along with the PSC as needed.

7 CHANGES IN THE PLANNED ANALYSES

The following are changes in the analyses compared to [Protocol Amendment 3 \(01 Ssep2016\)](#).

7.1 PFS-4 in Cohort 3A

PFS-4 rate in Cohort 3A has been added as an exploratory efficacy endpoint to further explore the efficacy of lenvatinib in combination with ifosfamide and etoposide in pediatric osteosarcoma subjects.

7.2 Analysis Sets

The following analysis sets have been included to help with analyses.

- Full Analysis Set
- Per Protocol Analysis Set
- Palatability Analysis Set

The DLT Analysis Set will be defined for Cohort 1 and 3A.

7.3 Proximal Tibial Growth Plates and Palatability and Acceptability Questionnaire

Because of small numbers of subjects, results for these two variables will be presented in subject listings and not formally analyzed.

8 DEFINITIONS AND CONVENTIONS FOR DATA HANDLING

8.1 Visit Windows

Visit windows will be defined to be upper and lower bounds of 1 day of the scheduled visit, following the protocol, which states that efforts should be made to conduct laboratory assessments and administer treatment on the day scheduled (± 1 day).

Tumor assessments for efficacy analysis are to be performed every 8 weeks (within Week 8) for Cohorts 1, 2A and 2B and every 6 weeks (within Week 6) for Cohort 3A and 3B (or sooner if clinically indicated) until documentation of PD.

In the calculation of descriptive statistics for laboratory values and vital signs, if a visit has multiple observations, the observation closest in date and time to the target visit day will be used in the analysis. If 2 or more observations have the same distance to the target visit day, the one that has the highest CTCAE grade or is farthest outside the normal range will be used. The purpose of this windowing is to provide a single record per subject per visit for the calculation of descriptive statistics and change from Baseline per visit. Other safety analyses (e.g., worst grade for laboratory results) will include all observations. All by-visit analyses will be performed using assessments at corresponding scheduled visits recorded in the eCRF. Data from all postbaseline assessments including those at scheduled and unscheduled visits will be used in the shift tables.

8.2 Safety and Efficacy Data Handling

8.2.1 Partial dates

Partial dates for AE and prior/concomitant medication, laboratory values, vital signs, and ECGs will not be imputed.

8.2.1.1 Diagnosis date

- If only the day of the month is missing, the 15th of the month will be used to replace the missing day
- If both the day and the month are missing, "July 1" will be used to replace the missing information

8.2.1.2 Date of Death

- If only the day of the month is missing, the 1st of the month will be used to replace the missing day
- If both the day and the month are missing, "Jan 1" will be used to replace the missing information
- If the entire date is missing, the date of death will be imputed as the last known date the subject was known to be alive + 1 day

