5.4.2.1 Primary Efficacy Analyses

COHORT 2A: DTC

The primary efficacy endpoint is ORR for subjects with measurable disease and BOR for all subjects. Tumor response will be based on RECIST 1.1 and assessed every 8 weeks. The analysis will be descriptively performed on the Full Analysis Set.

COHORT 2B: SINGLE-AGENT EXPANSION

The primary efficacy endpoint is the PFS-4 rate based on RECIST 1.1. This is the proportion of subjects free of progression at 4 months. The PFS-4 rate will be estimated using the binomial proportion and the corresponding 80% and 95% exact binomial distribution CIs ([Clopper and Pearson, 1934](#)) will also be provided. The PFS-4 rate will also be tested using a null hypothesis that the PFS-4 rate is $\leq 25\%$ tested against the alternative hypothesis of a PFS-4 rate $\geq 45\%$, using the 1-sample exact test of a single proportion, at the 1-sided 0.1 level. These analyses will be performed on the lenvatinib-naïve subjects in the Full Analysis Set and the Per Protocol Analysis Set.

The PFS-4 rate will be calculated using PFS-4 evaluable subjects. These are defined as follows.

PFS-4 evaluable subjects:

- includes subjects who were treated with study medication at least 16 weeks;
- includes subjects who died or radiologically progressed within 16 weeks after the first administration of study medication. These subjects are not considered free of progression at 4 months;
- includes subjects who received anticancer treatment within 16 weeks after the first administration of study medication. These subjects are not considered free of progression at 4 months;
- excludes those who discontinue the study due to AE or reasons other than disease progression, death, or receiving anticancer treatment within 16 weeks after the first administration of study medication;
- excludes subjects administered any study medication with no baseline or no postbaseline tumor assessments.

COHORT 3B: OSTEOSARCOMA COMBINATION EXPANSION

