8.2.1.5 Date of Start of Subsequent Anticancer Therapy

- When the day is missing, it is assumed that the subsequent therapy started on the first day of the given month if this day is later than the last dosing date. Otherwise, it is assumed that the subsequent therapy started on the day following the last dosing date.
- When the day and the month are missing, it is assumed that the subsequent therapy started on the first day of the given year if this day is later than the last dosing date. Otherwise, it is assumed that the subsequent therapy started on the day following the last dosing date.

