8.3.5 Last Known Alive Date

The last date the subject was known to be alive should be derived from survival follow-up date or the latest date among last treatment date, last radiologic follow-up date, last laboratory assessment date, last AE date, last concomitant medication date, or last vital sign measurement date.

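### SAP 8.2.1.2 imputes partial death dates without checking them against the last-known-alive date, so an imputed death can precede documented contact; an effect on PFS-4 is possible but rare

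*SAP*

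**What the plan says.** SAP 8.2.1.2 has three branches for an incomplete death date.

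- Day missing: "If only the day of the month is missing, the 1st of the month will be used to replace the missing day".
- Day and month missing: 1 January of the recorded year.
- Whole date missing: "the date of death will be imputed as the last known date the subject was known to be alive + 1 day".

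Only the third branch refers to when the subject was last known alive. SAP 8.3.5 derives that date from survival follow-up "or the latest date among last treatment date, last radiologic follow-up date" and the laboratory, adverse event, medication and vital sign dates.

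SAP 8.2.1.5 does put a lower bound on the start of subsequent therapy. If the 1st of the month or year is not later than the last dose, then: "Otherwise, it is assumed that the subsequent therapy started on the day following the last dosing date".

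SAP 8.2.1.3 and 8.2.1.4 compare imputed progression and scan dates with the death date only when the death date is complete, so they do not repair a partial one.

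For PFS-4 in Cohort 2B, SAP 5.4.2.1 defines the evaluable set by bullets. One "includes subjects who were treated with study medication at least 16 weeks". Another "includes subjects who died or radiologically progressed within 16 weeks after the first administration of study medication", and those subjects count as failures. Cohort 3B has the same bullets at 18 weeks. No order of precedence is given.

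**The concern.** The rule treats a better-documented death worse than an undocumented one. A death with no date at all cannot be placed before the last contact, but a death known to the month or year can be.

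A death dated before a recorded scan or dose is an impossible sequence. It shortens PFS and OS, and it shortens the follow-up at which TTP is censored for death. With 1 January it can give a negative time. It also enters SAP Table 3, rule 9, which censors a death that comes too long after the last adequate assessment: more than 125 days in Cohorts 1, 2A and 2B, or 97 days in Cohorts 3A and 3B. An early imputed death shortens that interval, or makes it negative, and can turn a censored subject into an event.

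For PFS-4, a subject treated past the landmark can also appear to have died before it, and so meet two conflicting bullets.

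**Working it through.** **1. Largest contradiction with recorded data.** The worst case is a last contact on the last day of the recorded period.
- Day missing: 31 − 1 = 30 days.
- Day and month missing: 31 December back to 1 January of the same year is 364 days, or 365 in a leap year (2016 falls in the study period).

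**2. Worked dates.** Days are counted from first dose. The landmark is 16 × 7 = 112 days in 2B and 18 × 7 = 126 days in 3B. The dates are illustrative and use the 2B landmark.

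| First dose | On drug, progression-free to | Death recorded as | Imputed death | Result |
|---|---|---|---|---|
| 20 Mar 2017 | 24 Jul 2017 (day 126) | July 2017 | 1 Jul 2017 (day 103) | 126 − 103 = 23 days before last contact, and before day 112 |
| 15 Oct 2017 | 20 Jun 2018 (day 248) | 2018 | 1 Jan 2018 (day 78) | 248 − 78 = 170 days before last contact, and before day 112 |
| 10 Mar 2017 | 20 Nov 2017 (day 255) | 2017 | 1 Jan 2017 (day −68) | before first dose; negative PFS and OS |

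In rows 1 and 2 the subject meets both the treated-16-weeks bullet and the died-within-16-weeks bullet. In row 3 the death is not within 16 weeks *after* first dose, so PFS-4 is undefined rather than a failure.

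**3. Rule 9 of Table 3.** With the day missing, the imputed date is up to 30 days before the true date. A true gap of 126 to 155 days (125 + 30) can therefore be read as 125 or less. On the 6-weekly schedule the range is 98 to 127 days (97 + 30).

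**4. How often the imputed date falls at or before the landmark, given a partial date.** The documents do not say how many dates will be partial. Assumptions: the true death is uniform over a window starting the day after week 16, and first-dose dates are spread evenly over four calendar years.

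| Window after week 16 | Day missing | Day and month missing | of which before first dose |
|---|---|---|---|
| 30 days | 49% | 96% | 65% |
| 182 days | 8% | 75% | 44% |
| 365 days | 4% | 50% | 24% |

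Subtracting the last column, a year-only date literally meets the within-16-weeks condition in about 31%, 31% and 26% of cases. The day-missing and day-and-month-missing shares are the same at 18 weeks; the before-first-dose share is slightly lower.

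**5. What one subject can decide.** The Cohort 2B design in SAP Section 4 reproduces. Let X₁ be the successes among the first 15 subjects and X₂ those among the next 12. The probability of declaring activity is the sum over x ≥ 5 of P(X₁ = x) × P(X₂ ≥ 10 − x). It is 0.0973 at 25% and 0.8012 at 45%, against the stated 0.1 and 80%. One lost success then matters only here:
- 2B final: 10/27 is active, 9/27 is not.
- 2B stage I: 5/15 continues, 4/15 suspends accrual.
- 3B with 15 evaluable: one-sided exact p against 25% is 0.057 at 7/15 and 0.148 at 6/15, either side of 0.1.

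**6. Effect of a floor.** A subject treated to the landmark has a last-known-alive date at or after it, so a death floored at that date cannot fall before the landmark. In row 1 the death moves from 1 July (day 103) to 25 July (day 127) and the subject remains a success.

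**The case against.** **The section is an outline.** SAP 5.3 calls the imputation conservative and leaves more detail to the dataset specifications. This stands: a floor may exist there, and those specifications are not among the documents. But 8.2.1.2 prints a complete rule, and a programmer following it would apply no floor. Conservatism can justify an early date among the possible ones, not a date that recorded data contradict.

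**The PFS-4 effect is remote.** This largely stands. With only the day missing, a reclassification needs the death in the landmark's own calendar month. It is then at most 30 days after the landmark, and so at most 30 days after the last dose. Adverse events are still collected in that period (Protocol 9.5.1.5), and deaths must be telephoned in immediately (Protocol 9.5.4.1). An unknown day of death is unlikely there. A year-only date is also unlikely while survival is checked every 3 months for a year (Protocol 9.1.3).

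**The error runs against the drug.** This stands wherever the outcome is defined: times get shorter, and successes can only be lost. OS is exploratory and untested in the SAP (5.1.3).

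**Last known alive plus 1 day can overshoot.** This stands. With a last contact on 30 November and death recorded as November, it gives 1 December. The fix needs a cap.

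**Conclusion.** The rule as printed can produce a death date that the trial's own records contradict. The contradiction is at most 30 days with the day missing and 364 or 365 days with day and month missing, and in the latter case the date can precede first dose. The SAP already has the date needed to prevent this and uses it in the neighbouring branch. This is a minor defect, worth correcting because the correction costs almost nothing.

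A reader might infer that the rule puts the primary endpoint at material risk by turning PFS-4 successes into failures. The documents do not support that. It takes a partial death date, a landmark between the imputed date and last contact, and a cohort at a boundary count, and prompt death reporting makes the first unlikely when the day alone is missing. Where 1 January precedes first dose, the result is an undefined outcome, not a failure. Nor is there ground to infer inflated false-positive findings, since a defined reclassification removes a success.

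The conclusion rests on the SAP text alone. The number of partial dates is unknown, the percentages in the working depend on the stated uniform assumptions, and a floor in the dataset specifications would settle the matter.

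**What to change.** In SAP 8.2.1.2, impute a partial death date as the later of (i) the current rule and (ii) the last-known-alive date of 8.3.5 plus 1 day, capped at the last day of the recorded month, or of the recorded year when the month is missing too. Take last known alive from complete dates only, because SAP 8.2.1 leaves partial adverse event and medication dates unimputed. If the cap applies because last contact was on the final day of the period, the imputed death falls on that day, which is the only date consistent with the record.

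As a parallel consistency rule, bound an imputed progression date in 8.2.1.3 from below at the day after the last assessment that did not show PD, with the same cap.

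The cost is one sentence per rule before database lock, plus a check that the dataset specifications agree. If they already contain a floor, it need only be stated in the SAP. No sample size, test or decision boundary changes.

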8.2.1.3 Date of Progression

- If only the day of the month is missing, the 1st of the month will be used to replace the missing day
- If the day and month are missing or a date is completely missing, it will be considered as missing and no date will be imputed

In case the date of death is present (complete date), the imputed progression date will be compared with the date of death. The earlier date of imputed progression date and date of death will be considered as the date of progression.

8.2.1.4 Date of Last Tumor Assessment

- If only the day of the month is missing, the 1st of the month will be used to replace the missing day
- If the day and month are missing or a date is completely missing, it will be considered as missing and no date will be imputed

In case the date of death is present (complete date), the imputed date for tumor assessment parameters will be compared with the date of death. The earlier date of the imputed date and date of death will be considered as the date of last tumor assessment.

8.2.1.5 Date of Start of Subsequent Anticancer Therapy

- When the day is missing, it is assumed that the subsequent therapy started on the first day of the given month if this day is later than the last dosing date. Otherwise, it is assumed that the subsequent therapy started on the day following the last dosing date.
- When the day and the month are missing, it is assumed that the subsequent therapy started on the first day of the given year if this day is later than the last dosing date. Otherwise, it is assumed that the subsequent therapy started on the day following the last dosing date.

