9.4.8.2 Prohibited Concomitant Therapies and Drugs

Subjects should not receive other antitumor therapies while on study. If subjects receive additional antitumor therapies, such as chemotherapy, hormone therapy with well-known direct antitumor activity against the subject's malignancy, palliative radiotherapy (other than as described below), or immunotherapy, this will be judged to represent evidence of disease progression, and study medication will be discontinued. These subjects should complete all off-treatment assessments and continue to be followed for survival in the Post-treatment Follow-Up.

Prophylactic use of G-CSF is not permitted during this study for Cohorts 1, 2A, and 2B. G-CSF is recommended for Cohorts 3A and 3B to mitigate the toxicity of ifosfamide and etoposide).

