5.3 Data Analysis General Considerations

For incomplete dates involving efficacy and other safety data, a conservative imputation will be used for calculation. See [Section 8.2.1](#) for the outline of imputation rules, which will be specified in the study analysis dataset specifications with more details.

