5.4.2.2 Secondary Efficacy Analyses

The secondary efficacy endpoints include BOR over the treatment period (except for Cohort 2A), ORR (except for Cohort 2A), DCR, and CBR, as well as DOR (measurable disease only). PFS and TTP are defined in SAP [Section 5.1](#) and will be performed for subjects in the Full Analysis and Per Protocol Analysis Sets.

Subjects who do not have a tumor response assessment for any reason will be considered nonresponders and will be included in the denominator when calculating the response rate. The count and percentage for ORR will be summarized by dose level for Cohorts 1 and 3A and by cohort for Cohorts 2B and 3B. ORR and corresponding 95% CI based on the exact binomial distribution will be estimated for all corresponding treatment cohorts.

The count and percentage for both the DCR and CBR will be summarized for each treatment cohort, along with the exact 95% CI for.

The median and quartiles of DOR will be estimated by the Kaplan-Meier (KM) method ([Kaplan and Meier, 1958](#)), and the 95% CI estimated with a generalized Brookmeyer and Crowley method ([Brookmeyer and Crowley, 1982](#)).

For PFS, if a subject has not experienced PD or death, then the subject's data will be censored on the date of the last adequate radiologic assessment.

TTP will be calculated using data from all subjects in the Full Analysis Set. The calculation for TTP does not classify deaths as events.

The PFS censoring rules in this SAP and definition of progression date follow the [Food and Drug Administration \(FDA\), Guidance for Industry Clinical Trial Endpoints for the Approval of Cancer Drugs and Biologics \(2007\)](#) (See SAP Table 3). The PFS censoring rules are referenced in SAP Table 3 and TTP censoring rules are referenced in SAP Table 4.

Table 3 Censoring Rules for Analysis of Progression-Free Survival

No	Situation	Date of Progression or Censoring	Outcome
1	No baseline tumor assessments	Date of first dose	Censored
2	No postbaseline tumor assessments	Date of first dose	Censored
3	Progression documented between scheduled visits	Date of first radiologic PD assessment	Progressed
4	More than 1 NE tumor timepoint assessment	Date of last adequate radiologic assessment before NE tumor assessments	Censored
5	No progression at time of data cutoff	Date of last adequate radiologic assessment	Censored
6	New anticancer treatment started	Date of last adequate radiologic assessment prior to or on date of new anticancer treatment	Censored

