7	Death before first tumor assessment	Date of death	Progressed
8	Death between adequate assessment visits*	Date of death	Progressed
9	Death or progression after more than one missed visit/tumor assessment**	Date of last adequate radiologic assessment before missed tumor assessments	Censored
10	Treatment discontinuation for reasons other than PD	Date of last radiologic assessment before treatment discontinuation	Censored

CR = complete response, NE = not evaluable, PD = progressive disease, PR = partial response, q6w = every 6 weeks, q8w = every 8 weeks, SD =stable disease.

* Adequate tumor assessment is radiologic assessment at regular interval as defined in the protocol.

** More than 1 missed visit/adequate tumor assessment is defined as having either 1 of the following 2 durations being longer than 18 weeks – 1 day, which is 125 days ($= ((8+1) \times 2 \times 7) - 1$) for subjects on the q8w tumor assessment schedule in Cohorts 1, 2A and 2B; while 14 weeks – 1 day, which is 97

days (= ((6+1) x 2 x 7) – 1) for subjects on the q6w tumor assessment schedule in Cohorts 3A and 3B:

- a. Duration between 2 consecutive tumor assessments
- b. Duration between the last adequate tumor assessment and death or PD

The priority of the censoring rules is as follows:

1. If the subject had PD or death, the following sequence will be applied:

- If a subject did not have a baseline or postbaseline tumor assessment (Nos. 1 and 2), the subject will be censored on the date of first dose. However, if the subject died within 125 days in Cohorts 1, 2A and 2B or 97 days in Cohorts 3A and 3B following the first dose and did not receive a new anticancer treatment, it will be counted as PFS event at the date of death. If a subject had new anticancer treatment before PD or death (No. 6), the subject will be censored on the date of the last adequate tumor assessment prior to or on the date of new anticancer treatment. If PD is reported after the drug discontinuation visit, the subject will be censored at the date of last radiologic assessment before drug discontinuation except when PD happened at the same visit as drug discontinuation (No. 10). If PD happened within 4 weeks of drug discontinuation (Week 16 for Cohort 2 and Week 18 for Cohorts 3A and 3B), it will be considered PD at drug discontinuation visit and counted as PFS event.

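### SAP 8.2.1.5 can place a partly dated new therapy before a documented PD, so that Kaplan-Meier PFS and TTP censor a true event

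*SAP*

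**What the plan says.** - **Imputation (SAP 8.2.1.5).** If only the day is unknown, the rule reads "it is assumed that the subsequent therapy started on the first day of the given month if this day is later than the last dosing" (that is, later than the last dose). With day and month missing, the first day of the recorded year is used on the same condition. In both cases the fallback is "Otherwise, it is assumed that the subsequent therapy started on the day following the last dosing date". The last dosing date is the only other date consulted.
- **PFS rules (SAP 5.4.2.2).** For subjects with PD or death the SAP sets out a sequence. In its first step, after the rule for missing tumor assessments, comes "If a subject had new anticancer treatment before PD or death (No. 6), the subject will be censored". Table 3, row 6, gives the censoring date: "Date of last adequate radiologic assessment prior to or on date of new anticancer treatment". Next comes No. 10, which censors PD reported after the discontinuation visit. It spares PD at that visit and PD within 4 weeks of discontinuation, of which the SAP says "it will be considered PD at drug discontinuation visit and counted as PFS event". The rule that takes the event date comes last.
- **TTP rules (same section).** No. 6 is repeated. The 4-week provision differs: here such a PD is censored at the discontinuation visit, so only PD no later than that visit remains an event.
- **Stated intent (SAP 5.3).** "For incomplete dates involving efficacy and other safety data, a conservative imputation will be used for calculation". The next sentence calls the rules in 8.2.1 an outline and leaves detail to the dataset specifications.
- **Neighbouring rule (SAP 8.2.1.3).** An imputed progression date is compared with the date of death. Section 8.2.1.5 has no such comparison with PD.

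**The concern.** No. 6 asks which came first, PD or new therapy. If the therapy date is partial, that order is decided by an imputation that picks the earliest date compatible with the last dose. A subject who stopped drug, had PD on the off-treatment scan and then moved to the next therapy can be recorded as having switched before progressing.

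The event is then replaced by censoring at an earlier scan. The censoring is informative, because it falls on subjects who have just progressed, and it pushes the PFS curve upward. For an endpoint that censors at new therapy, the earliest date is therefore not the conservative choice that SAP 5.3 promises.

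The date pattern is an ordinary one: SAP 3.3.5 allows the off-treatment procedures up to 30 days after the last dose, so a PD scan may well fall after it.

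**Working it through.** The plan states no figure for this point, so the rule itself is checked.

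**Notation.** L = last dosing date, P = documented PD, S = true therapy start, I = imputed start. By 8.2.1.5, I is the first day of the recorded month (or year) if that day is after L, and otherwise L + 1. No. 6 applies when I < P.

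**Step 1, bound.** I is never earlier than L + 1, so I < P requires P to be at least L + 2. PD on or before the last dose, or 1 day after it, is safe.

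**Step 2, examples.** In each case PD truly precedes the new therapy.

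| L | P | S | Recorded as | I | Result |
|---|---|---|---|---|---|
| 10 Jun | 20 Jun | 28 Jun | June | 11 Jun | before PD: censored |
| 25 May | 12 Jun | 26 Jun | June | 1 Jun | before PD: censored |
| 20 Jun | 20 Jun | 28 Jun | June | 21 Jun | event kept |
| 10 Jun | 20 Jun | 5 Jul | July | 1 Jul | event kept |
| 10 Jun | 20 Jun | 5 Jul | year only | 11 Jun | before PD: censored |

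In the censored rows PD is 10 or 18 days after last dose. If discontinuation is dated at the last dose, that is within 4 weeks, so the PD would count as a PFS event without No. 6.

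**Step 3, date patterns.** I let L run over every day of 2018 and took S at 1 to 28 days after P.

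- P from 14 days before L to 1 day after it: 0% have I before P.
- P 2 to 28 days after L, day missing: 135,351 / 275,940 = 49%.
- P 2 to 28 days after L, day and month missing: 264,222 / 275,940 = 96%.
- With the day missing, the share depends on the assumed delay from PD to new therapy: 84% for 1 to 7 days, 72% for 1 to 14 and 33% for 1 to 42.

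These are shares of assumed date combinations, given a partial date and a PD at least 2 days after last dose. They are not shares of patients.

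**Step 4, effect on the 4-month KM rate.** Assume 27 subjects (the evaluable target for Cohort 2B), 9 PDs at Week 8, 6 at Week 16 and no other losses. Week 16 is day 112. Four months are 4 × 30.4375 = 121.75 days by SAP 8.3.2, so the Week-16 PDs count.

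- All PDs kept: 18/27 × 12/18 = 44.4%.
- One Week-16 PD moved to censoring at Week 8: 18/27 × 12/17 = 47.1%.
- Two moved: 18/27 × 12/16 = 50.0%.

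**Step 5, the primary endpoint.** SAP 5.4.2.1 counts both radiologic progression and new anticancer treatment within 16 weeks (Cohort 2B) or 18 weeks (Cohort 3B) as failure. In the Step 4 cohort the binomial PFS-4 stays at 12/27 = 44.4% whichever date is used.

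**The case against.** **The detail may be elsewhere.** A comparison with PD may already be in the dataset specifications, which are not among these documents. That is possible. But 8.2.1.5 gives a complete rule, and a specification should not quietly reverse it.

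**The order of the rules can be disputed.** The 4-week sentence stands in the same bullet as No. 6 and treats the PD as occurring at the discontinuation visit. If that back-dating were applied first, a start imputed to the day after last dose need not precede the PD. The SAP announces a sequence and puts No. 6 earlier, which favours the reading used here, but it does not rank the two sentences explicitly. This part of the objection stands as a further reason to clarify the text.

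**The correction makes an assumption too.** When PD and new therapy share a recorded period, their true order is unknown. This stands, but weighs little: under SAP 3.3.5 post-treatment scans run only until progression or new therapy, so a documented PD in that period will usually have come first.

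**Stronger readings that the documents do not support.**
- A reader might infer that the primary endpoint loses events. Step 5 shows that it does not. An early imputed date could at most turn a non-evaluable subject into a PFS-4 failure, which lowers the rate.
- A reader might infer that every PD at least 2 days after last dose is lost when therapy starts in the same month. With last dose 25 February, PD 1 March and therapy recorded as March, the imputed start is 1 March, which is not before PD. PD more than 4 weeks after discontinuation, and not at that visit, is already censored by No. 10.
- A reader might worry about therapy recorded in a month wholly before the last dose, which the rule moves past it. Protocol 9.4.8.2 says of antitumor therapy on study that "this will be judged to represent evidence of disease progression, and study medication will be discontinued". Such a record is a protocol deviation or a data query, not a routine imputation case.

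**Conclusion.** The point holds within limits. A partial therapy start can be imputed before a documented PD, and No. 6 then turns a true event into censoring at an earlier scan. Three conditions are needed: a partial date, PD at least 2 days after last dose, and a PD that would otherwise be an event. For PFS, that last condition covers PD at the discontinuation visit or within 4 weeks of discontinuation. For TTP the exposure is narrower, because PD after that visit is censored anyway.

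Only the secondary Kaplan-Meier PFS and TTP analyses are affected, and the bias is upward. How many subjects are involved cannot be computed, since no frequency of partial dates is given. In a cohort of 27, each misclassified Week-16 PD moves the 4-month KM rate by about 3 points under the Step 4 assumptions. The conclusion rests on reading the priority list in the order in which it is written. It does not threaten the primary test, but the error is avoidable and should be corrected before the analysis.

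**What to change.** Amend SAP 8.2.1.5. When a documented PD falls in the recorded month, or in the recorded year if the month is also missing, set the imputed start to the latest of the first day of that period, the day after last dose, and the PD date itself. The PD date is enough, because a start on the same day does not precede PD, and it lies inside the recorded period.

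Add to the PFS and TTP priority rules that an imputed therapy date may not trigger No. 6 ahead of a documented PD in the same recorded period. In the PFS rules, also state how the 4-week provision ranks against No. 6.

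With the amended date rule, and true starts extended to 42 days after PD, none of the enumerated cases has an imputed start before PD. The cost is a few words of SAP text and one comparison in the date derivation, with no new data. The downside is that a PD which truly followed new therapy in the same period would be counted as an event. That should be rare, because scheduled scans stop when new therapy starts.
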